## **Introduction**

This document is a protocol for a human research study. This study is to be conducted in accordance with AH institutional research requirements and all federal regulations.

## **Background Information and Scientific Rationale**

Screening for cancer in asymptomatic adults can lead to early detection, which has a notable impact on the cost of care and on patient outcomes. It is estimated that in the first year after diagnosis (2017), the cost of treating Stage IV cancer, compared to Stage I, is increased per patient by \$37,661 for breast cancer, \$18,086 for prostate cancer and \$33,128 for lung cancer (Kakushadze, Raghubanshi, & Yu, 2017). Adjusting for inflation (2024), those approximate cost increases per patient would be \$48,959 for breast cancer, \$23,512 for prostate cancer and \$43,066 for lung cancer.

In addition, patients who are uninsured are significantly more likely to receive a late-stage diagnosis. In Florida, uninsured patients were 46.9% more likely to be diagnosed with a high-grade lung cancer, 50% more likely to be diagnosed with late-stage breast cancer, and 39% more likely to be diagnosed with late-stage prostate cancer (Sasaki, Parianos, & Rahman, 2021). Those in high poverty areas in Florida, both rural and urban, have increased likelihoods of late-stage diagnoses, and the overall cancer-related mortality rate was 22% higher in high poverty areas than in low poverty areas, including lung (risk ratio 1.24), breast (risk ratio 1.17), and prostate (risk ratio 1.29) cancers (Hall et al., 2022; Hall et al., 2023).

In terms of mortality, the overall survival rates for early stage compared to late is 99% to close to 30% for breast cancer, 64.4% to 7.6% for lung cancer, and 100% to 33.5% for prostate cancer (National Cancer Institute, 2024). In light of this, uptake in screening and early diagnosis could have tremendous impact on cancer survival outcomes for this vulnerable and underserved population.

Advances in novel and innovative approaches to cancer treatment are saving and improving lives. However, racial and ethnic minority groups and medically underserved populations continue to experience multilevel barriers to screening, timely diagnosis, and access to treatment. Integrating an Implementation Science framework is an opportunity to promote the adoption, use, and sustainability of interventions and clinical trials in community-based clinical settings to improve uptake of cancer screening, preventive services, timely follow-up of abnormal findings, and referral to accessible care among adults experiencing social and structural barriers to health.

This proposal aims to reduce disparities in cancer care and outcomes for underserved Central Florida adults by increasing rates of lung, breast, and prostate cancer screenings. Distrust and lack of access to primary care are barriers to screenings and early detection. Collaborating with established community organizations and identifying reasons to accept or decline care will allow us to offer sustainable community-based cancer screenings that result in increased cancer diagnosis and treatment.

We hypothesize that implementation of a community-based multi-disciplinary navigation team will foster improved cancer screening rates, financial navigation to facilitate timely definitive diagnosis and treatment regimens, as well as screening for clinical trial eligibility among underserved individuals. Effective patient navigation promotes access to timely treatment by overcoming barriers to care. Hospital-based patient navigation programs for cancer and chronic diseases have been well-established in improving screening rates and diagnostic resolution (Chen et al., 2024). Cancer-related financial hardship is an additional result of cancer diagnosis and treatment, and therefore of increased national interest (SWOG Cancer Research Network, 2024). While some oncology clinics provide financial navigation services, few community-based health care clinics have sufficient resources to proactively facilitate financial counseling and assistance ultimately delaying cancer screening, definitive diagnosis, and successful treatment (Bell-Brown et al., 2023).

## **Study Objectives**

### **Primary Objective/Aim/Goal/Hypothesis**

To evaluate a community-based outreach initiative for screening, diagnosis, and treatment of breast, lung, and prostate cancers in underserved adults using the RE-AIM implementation science framework.

### **Secondary Objective/Aim/Goal/Hypothesis**

Secondary goals include:

- To identify differences between adults who accept or decline cancer follow-up diagnosis and treatment, and clinical trial screening
- To identify barriers and facilitators to cancer screening, diagnosis, treatment, and clinical trial screening
- To understand perceptions towards navigators in the cancer care continuum

## **Study Design**

### **Research Design**

The research strategy will employ a prospective, mixed methods implementation science design based on the Reach, Effectiveness, Adoption, Implementation, and Maintenance (RE-AIM) framework.

Reach will include the number of patients in the community that are offered and undergo cancer screening. Effectiveness will be determined by comparison of monthly breast, lung, and prostate cancer screening referral uptake to baseline. Adoption will be evaluated by the number of patients with positive screens that are referred for screening and for treatment. Implementation will occur via the cyclical improvement triad approach that includes repeated evaluation and modification to ensure that barriers to care are addressed. Maintenance and sustainability will be supported by the return on investment by early cancer detection and treatment.

## Research Intervention Description

The proposed intervention integrates cancer screenings at pop-up clinics located at community resource spots in partnership with well-established community-based organizations for the underserved, as well as in local emergency departments that serve this population. Currently, cancer screenings are offered as standard of care in primary care settings; however, this population rarely has access to primary care. Instead, this population often seeks episodic care for symptom management and does not benefit from preventive care services in primary care settings. Integrating cancer screenings into episodic care will be accomplished through a multi-faceted approach which includes leveraging a team of navigators to help connect those with positive screening results to community health resources, treatment financial advocacy, care coordination, and access to screening for clinical trials. Navigators will guide access to a continuum of care including diagnosis, treatment, and clinical trials.

National guidelines exist for primary care providers to conduct annual screenings to detect and treat common cancer tumors before they progress to systemic disease. These guidelines are not routinely followed in non-primary care settings, like pop-up clinics and emergency rooms. The study team will provide education to community-based healthcare providers on United States Preventive Services Taskforce Screening Guidelines for breast, lung, and prostate cancers. The USPSTF recommends annual screening for lung cancer with low-dose computed tomography (LDCT) in adults aged 50 to 80 years who have a 20 pack-year smoking history and currently smoke or have quit within the past 15 years. The USPSTF recommends biennial screening mammography for women aged 40 to 74 years. The USPSTF recommends that the decision to undergo periodic prostate-specific antigen (PSA)-based screening for prostate cancer should be an individual one among men aged 55 to 69 years. All participant-facing education materials will be reviewed and approved the Institutional Review Board (IRB) before use in the research study.

Screenings will take place at pre-established pop-up clinics associated with community-based outreach organizations or other settings such as emergency departments and urgent care centers where patients may show for symptom management and result in a positive screen. A bilingual field- and a bilingual hospital-based navigator will connect participants with screening (e.g. mammograms) and confirmatory diagnostics, treatment and/or clinical trials when applicable. In addition, a financial navigator will identify free and reduced cost diagnostic testing and assist with Medicaid enrollment and other financial aspects of care for patients who screen positive.

## Study Site(s)/Location(s) and Number of Subjects

*AdventHealth sites (hospital(s), campus, physician offices, etc):* AdventHealth Central Florida Division (e.g., AdventHealth Apopka, AdventHealth East Orlando, AdventHealth Kissimmee) emergency departments, CentraCare locations

*Estimated number of subjects at AdventHealth sites:* Unable to determine until screenings provided

*Name of external site(s) outside of AdventHealth:* Community health clinics or health systems willing to provide free or low-cost diagnostics to under-resourced patients on referral

*Estimated number of subjects at external sites:* Unable to determine until screenings provided

*Total number of all sites:* 20

*Estimated number of subjects at all sites combined:* 200

## Multi-Site Research Logistics/Communication Plan

N/A

## Research Conducted in a Foreign Country

N/A

## Community-Based Participatory Research

N/A

## Subject Selection

### Vulnerable Populations (if applicable)

N/A

### Inclusion Criteria

The inclusion criteria for patients will be the following:

1. Adult aged 18 or older
2. Seeking care at a CRS or emergency department
3. Meets criteria for lung, breast, and/or prostate cancer screening, as outlined below:
  - a. Lung cancer: Adults aged 50 to 80 years who have a 20 pack-year smoking history and currently smoke or have quit within the past 15 years
  - b. Breast cancer: Women aged 40 to 74 years
  - c. Prostate cancer: Men aged 55 to 69 years
4. Receives a positive screening result for lung, breast, and/or prostate cancer at a study site

The inclusion criteria for stakeholders will be the following:

1. Speaks English or Spanish through study interpreters
2. Able to attend 75% or more of scheduled meetings
3. Must be key individuals providing critical services to address food insecurity, employment assistance, government support, mental and physical health, and health education within identified Community Resource Spots, emergency departments, and urgent care centers.

## Exclusion Criteria

The exclusion criteria for patients will be the following:

1. Displays behavior disruptive to other patients or staff
2. Refusal to accept screening for breast, lung, and/or prostate cancers

The exclusion criteria for stakeholders will be the following:

1. Speaks language other than English or Spanish
2. Unable to attend 75% or more of stakeholder meetings

## Resources Available

### Research Personnel Qualifications

All members of the study team are employed by AdventHealth in full-time positions with training in research processes and methodologies. All personnel have completed the necessary AdventHealth IRB training and credentialing requirements. A study start-up meeting will be held to describe the research study and clarify each team member's duties and functions. Biweekly meetings will be held either in person or by teleconference for the duration of the study to review the study and to ensure that the protocol is being followed, report the study progress, share reportable information, and implement any amendments made to the protocol.

The research team will be comprised of a principal investigator, implementation scientists, qualitative researcher, RN clinical research study coordinator/clinical educator, statistician, project managers, cancer care navigator, financial navigator, research trials navigator, community outreach coordinator, advanced practice provider (APP), data manager, and information architect. As these individuals are hired and/or added to the research team, the delegation log will be revised to include them.

## Study Procedures

### Subject Recruitment and Screening

#### Recruitment of Stakeholders

Investigators will establish relationships with community stakeholders, providers, and other key personnel to inform them of the program, the study, and opportunities to engage in stakeholder focus groups to provide feedback about program operations. For those interested in participating, a study team member will explain the study and the requirements for participation, review the informed consent form in detail, and obtain consent.

#### Recruitment of Patients

Patients undergoing screening as standard of care will have access to clinic-based educational materials, i.e. signage and pamphlets in English and Spanish on cancer screening, diagnosis and care and on the study opportunity.

As standard of care for patients who screen positive, a care navigator will be assigned. The care navigator will provide patients with study recruitment materials and information, ensuring patients are aware that study involvement does not impact care navigation or treatment.

After positive breast, lung, and/or prostate cancer screening in the field or at an emergency room or care facility, study team members will be informed of positive field screens. Patients with positive screens will be referred for confirmatory diagnostic testing and will receive guidance from care navigator and the financial navigator to set up appointments. A study team member will meet the potential participant at the site of diagnostic testing and/or at emergency departments or other urgent care sites to introduce the study and obtain informed consent for research activities.

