### **Consent Process**

The researchers will follow SOP CW AHC 216 Informed Consent Process and Written Documentation of Informed Consent. Also, the researchers will follow SOP CW AHC 249 Remote and Electronic Methods for Conducting Informed Consent in Non-Exempt Research.

**For Patients:** Upon referral for definitive diagnosis based on their cancer screening results, patients will be contacted by a study team member for informed consent for survey completion, interviews and electronic health record access to monitor outcomes. All consent forms will be completed on paper or electronically via REDCap on a tablet device provided by the study team.

**For Stakeholders:** Study team members will contact community stakeholders in person, or via phone or email to re-explain the study and obtain consent. Consent forms may be completed on paper or electronically via REDCap.

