**Study Visits**

For patients, study visits include:

- Consent and enrollment and at the site of confirmatory diagnostics and/or emergency room or healthcare center

- 1 or more interviews with the research team throughout the study period
- Survey package completion with coordinator at a site of diagnosis or care

Study Visit	1	2	3	4	5	6	7	8
Consent/Enrollment	X							
Baseline Surveys		X						
First Interview			X					
3-Month Surveys				X				
Optional Follow-Up Interviews					X	X	X	X

For stakeholders, study visits include:

- Consent and enrollment
- Ongoing stakeholder meetings throughout the duration of the study up to 12.
- 1 or more interviews with the research team throughout the study period.

Study Visit	1	2	3	4	5	6	7	8	9	10	11	12	13	14	15	16	17	18
Consent/Enrollment	X																	
Stakeholder Meetings		X	X		X	X		X	X		X	X		X	X		X	X
First Interview				X														
Optional Follow-Up Interviews							X			X			X		X			

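### Consent is placed at diagnostic, emergency or urgent care sites in two sections but at referral in a third; following the first two would under-represent patients who decline follow-up diagnosis

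*Protocol*

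**What the plan says.** Three Protocol sections govern when and where a screen-positive patient is asked to join.

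- **Recruitment of Patients:** "A study team member will meet the potential participant at the site of diagnostic testing and/or at emergency departments or other urgent care sites", and the purpose of that meeting is "to introduce the study and obtain informed consent for research activities". The same section says "The care navigator will provide patients with study recruitment materials and information" and that "study team members will be informed of positive field screens".
- **Study Visits:** the first patient visit is "Consent and enrollment and at the site of confirmatory diagnostics and/or emergency room or healthcare center", and a later item is "Survey package completion with coordinator at a site of diagnosis or care".
- **Consent Process:** "Upon referral for definitive diagnosis based on their cancer screening results, patients will be contacted by a study team member for informed consent". No place is given. The section cites an SOP on "Remote and Electronic Methods for Conducting Informed Consent in Non-Exempt Research", but says patient forms are completed on paper or on a tablet that the study team provides.

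Pop-up clinics are the first-named screening setting in Research Intervention Description. Recruitment of Patients does not name them as a place of consent. The Secondary Objective section aims to find differences between adults who accept and adults who decline follow-up diagnosis, treatment and clinical trial screening.

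**The concern.** The diagnostic testing site is a place that a patient who declines diagnostics does not visit. If the study is introduced and consent taken there, enrolment depends partly on the behaviour that the secondary objective wants to compare. Surveys, interviews and health record access all follow from that consent. The consent and HIPAA waivers are marked not applicable, so the Protocol states no individual-level data route for a decliner who is never approached.

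At stake is the accepter-decliner comparison at the diagnosis step. Decliners would be too few among enrollees, and those enrolled might be untypical, for example by screening setting. Their barriers to care, which the outreach is meant to learn about, would be under-heard. Analysis cannot recover people who were never approached.

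**Working it through.** **Step 1: follow each kind of screen-positive patient through the text.**

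| Patient | Under Recruitment of Patients and Study Visits | Under Consent Process |
|---|---|---|
| Pop-up screen, attends diagnostics | Met at the diagnostic site | Contacted at referral |
| Pop-up screen, declines or never attends | No clearly listed meeting place, unless the undefined healthcare center covers pop-up clinics or the patient later comes to an emergency or urgent care site | Contacted at referral |
| Emergency or urgent care, result known during the visit, declines | Can be met there | Contacted at referral |
| Emergency or urgent care, screening completed by referral, declines diagnostics | May have left before the result is known | Contacted at referral |
| Attends diagnostics, later declines treatment or trial screening | Already met | Already contacted |

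The fourth row is possible because Research Intervention Description has navigators connect people with screening such as mammograms, and the Reach metrics count screening at point of care or by referral. The last row confines the problem to the diagnosis step.

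**Step 2: illustration of direction and possible size.** The Protocol gives no figure to reproduce, and every input here is assumed. Let p be the pop-up share of screen-positives and d the proportion declining diagnostics, equal in both settings. Let a and b be the chances that a pop-up decliner and an emergency or urgent care decliner enrol, relative to an accepter. Put m = pa + (1 − p)b. Then:

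- decliners among enrollees = dm / (dm + 1 − d)
- pop-up share of enrolled accepters = p
- pop-up share of enrolled decliners = pa / m

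With p = 0.5 and d = 0.3:

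| a | b | m | Decliners among enrollees | Pop-up share of decliners | Gap from accepters (50%) |
|---|---|---|---|---|---|
| 1 | 1 | 1 | 0.300/1.000 = 30.0% | 50.0% | 0 |
| 0.5 | 1 | 0.75 | 0.225/0.925 = 24.3% | 33.3% | 16.7 points |
| 0.25 | 1 | 0.625 | 0.1875/0.8875 = 21.1% | 20.0% | 30.0 points |
| 0 | 1 | 0.5 | 0.150/0.850 = 17.6% | 0% | 50.0 points |
| 0.5 | 0.5 | 0.5 | 0.150/0.850 = 17.6% | 50.0% | 0 |
| 0.25 | 0.25 | 0.25 | 0.075/0.775 = 9.7% | 50.0% | 0 |

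Other pop-up shares, with a = 0.25 and b = 1: at p = 0.3 the decliner share is 0.075/0.775 = 9.7% against 30% of accepters; at p = 0.7 it is 0.175/0.475 = 36.8% against 70%.

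**Step 3: reading the table.** Decliners are under-represented in every row where a or b is below 1. A gap by setting appears only where a and b differ. The first result needs only that decliners are harder to reach; the second needs them to be harder to reach in one setting than in the other.

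**The case against.** The strongest reply is that the sections fit together: contact at referral, then signing at a later meeting. Navigators hand out study materials, the team hears of positive field screens, a remote consent SOP is cited, and Study Duration foresees enrolled participants who decline further care. Much of this stands. A reader might infer that the sections flatly contradict each other, or that pop-up decliners are shut out, and the text supports neither. But Recruitment of Patients puts the introduction of the study itself at the later meeting, and handing out materials is not a consent approach. Citing the SOP also does not settle how patients are reached. Consent Process allows phone or email contact for stakeholders and does not say so for patients.

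A second reply is that a setting imbalance requires emergency and urgent care decliners to be approached as readily as accepters. No section says this, and screening by referral makes it doubtful. This stands fully: the 16.7, 30.0 and 50.0 point gaps come from setting b = 1.

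A third is that Secondary Objective Analysis plans thematic analysis of transcripts and observations and states no comparison of proportions, and that the patient sample is a convenience sample. This also stands, so no bias in a particular estimate can be claimed. It does not remove the concern, because themes about declining still depend on decliners being approached.

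Finally, a community resource spot can count as a site of care, since the Inclusion Criteria speak of seeking care there. That weakens the point about survey location, but the place of consent remains unclear.

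**Conclusion.** The point holds in a limited form. The place rule and the time rule are unreconciled. If the place rule is followed, patients who decline or never attend follow-up diagnosis are less likely to be approached, surveyed or interviewed. They would then be under-represented in a comparison that the Protocol sets as a secondary objective, possibly unevenly by setting.

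It would be tempting to conclude that enrolled decliners will come mainly from emergency and urgent care sites, and that setting differences will pass for accepter-decliner differences by a known amount. The documents do not support that, because they do not show that decliners are easier to reach in those settings. If Consent Process governs and contact is made in every setting, most of the selection disappears. The size cannot be derived from the documents. The illustrated 9.7% to 24.3% against a true 30% rests wholly on the assumed p, d, a and b.

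**What to change.** - In Recruitment of Patients, Consent Process and Study Visits, state one rule: contact and consent at referral, before the diagnostic appointment, in every screening setting. Include pop-up clinics, or remote consent under the SOP already cited.
- In Study Visits, allow surveys to be completed away from a site of diagnosis or care. Data Quality already makes them electronic through REDCap.
- As a refinement of the planned dashboard, report aggregate counts of all screen-positives by accepted or declined status and by screening setting. The dashboard already plans to describe participants and non-participants. Confirm the basis for these counts with the IRB, because the consent and HIPAA waivers are marked not applicable.

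The counts are needed because some decliners will also refuse research consent. The illustrative row with a = b = 0.5 shows that equal reluctance in both settings leaves no setting gap but still lowers decliners to 17.6% of enrollees.

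The cost is protocol wording and an IRB amendment. Navigators, the SOP, REDCap and the dashboard are already planned. The small downside is more follow-up contacts for people who consent earlier and then do not attend.
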